## 13 Ethics/Protection of Human Subjects

This study is to be conducted according to applicable US federal regulations and institutional policies (which are based in federal regulations, guidance, and ICH Good Clinical Practice guidelines).

This protocol and any amendments will be submitted to the Boston Medical Center and Boston University Medical Campus IRB, for formal approval of the study conduct. The decision of the IRB concerning the conduct of the study will be made in writing to the investigator.

All subjects for this study will be provided a consent form describing this study and providing sufficient information for subjects to make an informed decision about their participation in this study. The consent form will be submitted with the protocol for review and approval by the IRB. The consent of a subject, using the IRB-approved consent form, must be obtained before that subject is submitted to any study procedure. Consent will be documented as required by the IRB.

15.2 Case Report Forms (CRF)

15.2.1 Eligibility Assessment Form

Study Name:	Glaucoma Drop Aids
IRB Protocol #:	H-34905
Protocol Version # and/or Date:	
Principal Investigator:	[name]

SUBJECT # _____				
INCLUSION CRITERIA Must be "yes"	Yes	No	Location of supporting source documentation	Notes
1. Age 18 years or greater				
2. Patient of Boston University Eye Associates				
3. Currently on the same topical ophthalmic medications for treatment of glaucoma for minimum of two months				

15.2.3 Home Study Diary

**Individual(s) completing this form:**  Study Subject  Research team member: \_\_\_\_\_ (initials)

**Date of completion:** \_\_\_\_\_

Study ID	
Medication Name: _____	Start Date: _____  End Date: _____
Medication Name: _____	Start Date: _____  End Date: _____
Medication Name: _____	Start Date: _____  End Date: _____

*Please complete this paper and bring it to your next eye appointment along with your drop aid and eye drops*

15.2.4 Satisfaction Survey

**Study ID:** \_\_\_\_\_

**Name of study team member completing this form:** \_\_\_\_\_

**Date:** \_\_\_\_\_

**Study Visit:**     3-week phone call         Follow-up clinic visit

1. Do you like the drop aid?
  - a. Yes
  - b. No
  - c. I am not on a drop aid
  - d. I did not use the drop aid
2. Is it easier to instill drops with the help of the drop aid compared without the drop aid?
  - a. Yes
  - b. No
  - c. I am not on a drop aid
  - d. I did not use the drop aid
3. How many times did you miss instilling drops with the help of drop aid?
  - a. None
  - b. 1
  - c. 2
  - d. 3 or more
  - e. I am not on a drop aid
  - f. I did not use the drop aid
4. How many times do you miss instilling drops just using your glaucoma drops?
  - a. None
  - b. 1
  - c. 2
  - d. 3 or more
5. Would you use the drop aid long term?
  - a. Yes
  - b. No
  - c. I am not on a drop aid
  - d. I did not use the drop aid

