#### 4.2.2 Secondary Outcome Measures

The following secondary outcomes will also be measured:

1. Number of times a patient missed their eye when instilling eye drops
2. Patient satisfaction responses with treatment arms
3. Intention to use a drop aid long term

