## 9.3 Follow-Up Study Visits

### 9.3.1 3 Week Phone Call:

- Subject will complete satisfaction survey for all drop aid treatment or control groups over the phone
- Confirm next SOC clinical visit

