### 12.1.3. Secondary Objective: Patient Satisfaction

Formal hypothesis: Drop aid devices will prove greater patient satisfaction than administrations without a drop aid device.

Testable hypothesis: Mean patient satisfaction to those assigned to a drop aid device compared to mean patient satisfaction scores to those not assigned to a drop aid device.

Null hypothesis: Patients assigned to a drop aid device will not show greater patient satisfaction than patients not assigned to a drop aid device.

Alternate hypothesis: Patients assigned to a drop aid device will show greater patient satisfaction than patients not assigned to a drop aid device.

$$H_0: \mu_s < \mu_{sd} - \delta$$

$$H_A: \mu_s \geq \mu_{sd} - \delta$$

Where  $\mu_s$ , is the mean patient satisfaction without the drop aid device,  $\mu_{sd}$  is the mean patient satisfaction with the drop aid device.

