## 12.2 Sample Size Determination

The sample size was determined by the maximum number of subjects which could be randomized given the budgetary constraints of the grant funding. It was determined that a total of ten patients per group was financially feasible, thus a total of 40 patients will be enrolled in this study in approximately 1 year.

Enrolling the projected 40 subjects in 1 year is feasible, as the ophthalmology department sees approximately 275 glaucoma patients weekly. Due to the high volume of the glaucoma clinic, the study team should be able to easily recruit their target. Additionally, the study team is comprised of multiple

investigators and research assistants who have been delegated tasks on this protocol which can provide full-time recruitment coverage.

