### 12.3 Statistical Methods

A variety of statistical analysis will be used to analyze the results. A paired t-test will be the primary method of analysis. Any significant differences measured will be between the pre and post intervention, with the patient serving as their own control. However, the analysis will not be limited to a paired t-test and will also likely include ANOVA, chi-squared, p-value, linear regression, among others. Other outcomes such as length of time until completion of drops will also be measured and compared to no drop aid controls. Significant differences will be measured with similar statistical analysis as stated previously. Satisfaction of use will be measured with a survey and results will be averaged among those in the same cohort. Any significant differences will also be measured with similar statistical analysis stated previously.

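### The survey gives controls no satisfaction item they can answer, so the between-arm satisfaction hypothesis (12.1.3) cannot be tested as written; the missed-drops comparison (12.1.2) is computable but rests on differently worded items

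*Combined protocol and SAP*

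**What the plan says.** - **Hypothesis.** Section 12.1.3 takes the mean satisfaction of patients assigned to a device, "compared to mean patient satisfaction scores to those not assigned to a drop aid device". Its verbal null is: "Patients assigned to a drop aid device will not show greater patient satisfaction than patients not assigned to a drop aid device". Section 4.2.2 lists the outcome as "Patient satisfaction responses with treatment arms".
- **Who is surveyed.** Section 9.3.1: "Subject will complete satisfaction survey for all drop aid treatment or control groups over the phone". Section 9.3.2 repeats the survey in person at the final visit.
- **Analysis.** Section 12.3: "Satisfaction of use will be measured with a survey and results will be averaged among those in the same cohort". It gives no score and no coding of the response options. The same section describes the main analysis as pre-post, "with the patient serving as their own control".
- **Instrument.** Section 15.2.4 prints five multiple-choice items, the first being "Do you like the drop aid". Four of the five offer an option for patients who are not on an aid.
- **A narrower objective.** Section 4.1 speaks only of satisfaction with the patient's drop aid.
- **Size.** Section 12.2: "a total of ten patients per group was financially feasible", with 40 patients in all.

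**The concern.** A between-arm comparison of means needs a measurement in both arms. Here the form handed to controls asks for their opinion of something they were not given. If the plan is followed exactly, the control cohort average is either empty or depends on how a not-applicable answer happens to be coded. One of the stated secondary hypotheses would then have no data on one side, or a value produced by coding rather than by patients.

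Missed drops carry a milder form of the same problem. Device patients and controls report on their assigned method through two different questions, so a difference between arms could reflect the wording as well as the device.

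**Working it through.** **1. Planned size.** Section 12.2 gives 4 groups × 10 = 40, which reproduces the stated total: 10 controls and 3 × 10 = 30 device patients. The number was set by budget, so there is no power calculation to reproduce.

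**2. What a control can answer (15.2.4).**

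| Item | Subject | Substantive answer for a control? | Satisfaction item? |
|---|---|---|---|
| 1 | Liking the aid | No, only the not-on-an-aid option | Yes |
| 2 | Ease with the aid versus without | No, only the not-on-an-aid option | Yes (ease) |
| 3 | Misses with the aid | No, only the not-on-an-aid option | No |
| 4 | Misses with the bottle alone | Yes | No |
| 5 | Willingness to use the aid long term | No, only the not-on-an-aid option | Yes (intention) |

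A control can score 0 of the 3 satisfaction-type items. The home diary (15.2.3) records only medication names and start and end dates, and no other satisfaction measure is described. Usable control scores for 12.1.3 are therefore 0 of 10. Section 12.1.4 (long-term use) concerns device patients only and is not affected.

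**3. Averaging by cohort.** The documents give no scoring rule. If the not-on-an-aid answer is excluded, the control mean has no observations. If it were counted as not-yes, controls would score 0 of 10 by construction. The second case is an illustration only; the documents do not suggest that coding.

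**4. Missed drops (12.1.2).** For the assigned method, device patients use item 3 (past tense, with the aid) and controls use item 4 (present tense, bottle alone). The two share the categories none, 1, 2, and 3 or more, so an ordinal or chi-squared comparison can be computed. There are four limits:
- The wording and tense differ between arms.
- Neither item has a recall period.
- The top category is open, so a true mean count cannot be obtained.
- The phrase used for missing can be read as a skipped dose, whereas 4.2.2 defines the outcome as missing the eye.

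Item 4 has no not-applicable option, so device patients answer it too. For them it describes use without the assigned aid, and it does not replace item 3 in the between-arm contrast.

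**5. Precision if a common satisfaction item is added.** Assume equal SDs, all patients answering, and devices pooled against control (10 v 30).
- SE = √(1/10 + 1/30) = 0.365 SD.
- Welch df = (1/10 + 1/30)² / [(1/10)²/9 + (1/30)²/29] = 0.017778 / 0.001149 = 15.5.
- 95% half-width = t(0.975; 15.5) × 0.365 = 2.126 × 0.365 = 0.78 SD.
- On a 5-point item with an assumed SD of 0.8 to 1.2, this is 0.62 to 0.93 points.

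**The case against.** **Section 4.1 asks only about satisfaction with the aid.** This is true, and the survey serves that objective in the device groups. But 12.1.3 states its testable, null and alternate hypotheses against patients without a device, and 4.2.2 refers to treatment arms. The two sections have to be reconciled, and a text edit is enough to do it.

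**Patients are their own controls (12.3), and item 2 asks about ease with versus without the aid.** This also stands, and it partly answers the formal hypothesis in 12.1.3. It is a within-patient rating by device users, however, and supplies no control mean.

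**Controls do have a response option.** They do, and it is separate from No. Section 11.3 also separates not-applicable from not-done entries on case report forms. A reader might infer that the plan would count controls as dissatisfied and so manufacture a benefit for the devices. The documents do not support this: they give no scoring rule in either direction. The gap is the missing rule.

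**Missed drops.** A reader might infer that 12.1.2 also cannot be tested. It can be computed, and items 3 and 4 can be compared within device patients. Section 4.2 says the survey assesses precision, which favours the missing-the-eye reading. What remains is the unequal wording between arms.

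**The printed formula.** The H0 of 12.1.3 says the reverse of the verbal null beside it, and delta has no value. A reader might infer that a real benefit would be tested in the wrong direction. That would require someone to test the formula rather than the words, with an assumed delta and a score that does not yet exist. It is a separate correction.

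**Conclusion.** The point holds for satisfaction: as written, 12.1.3 has 0 of 10 usable control scores and cannot be tested between arms. This follows from the printed form and needs no numerical assumption. It is worth fixing, but it is confined to one secondary hypothesis and the instrument meant to serve it.

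Missed drops is a lesser point. The comparison exists, but its items differ between arms, and the documents give no basis for the size or direction of any wording effect.

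The count of 10 controls and the 0.78 SD half-width rest on ten per group in 12.2, which agrees with the four groups in Section 5. The equal-chance sentence in Section 5 lists Arm A and Arm B and could be read as 1:1 between arms. That wording should be reconciled with 12.2. Under either reading no control can supply a satisfaction score.

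The primary IOP outcome is not affected.

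**What to change.** Choose one of two routes for satisfaction.

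- **(a) Change the form.** Add one item worded identically for all four groups, asking how satisfied the patient is with the way they currently put in their drops, on an ordered scale (for example 5 points). Use it for 12.1.3. Report the difference, devices pooled minus control, with a Welch 95% confidence interval, and read it as an estimate.
- **(b) Change the text only.** Restate 12.1.3 as a descriptive device-group outcome in line with 4.1, and draw no between-arm conclusion on satisfaction.

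Under either route:
- State that the not-on-an-aid option is not applicable and is excluded from averages. Report patients who did not use their aid as their own category.
- Where feasible, replace the item 3 versus item 4 contrast with a single missed-the-eye item worded identically for all groups, with a fixed recall period. Analyse it with a rank-based or ordinal comparison; a percentile bootstrap is unreliable with 10 controls.
- Reconcile the allocation wording of Section 5 with 12.2.
- As a separate correction, make the formula in 12.1.3 match its verbal hypothesis, and either define delta or remove it.
- If items are added, amend the description of the survey in 4.2.

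**Cost.** Route (a) means a slightly longer form that the team wrote itself, matching edits to Sections 4.2 and 12, and a minor IRB amendment. Surveys already completed cannot supply the new items, and with 10 controls the estimate stays wide. Route (b) is a text edit, and it gives up the between-arm comparison.

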## 4 Objectives

### 4.1 Study Objectives

The primary objective of this study is to compare efficiency of various drop aids for glaucoma medications objectively via changes in intraocular pressure. The different drop aids that are utilized are the Simply Touch Eye Drop Applicator, the Fabrication Autodrop Eye Drop Guide, and the Owen Mumford OP 6100 Autosqueeze. The central hypothesis is that the use of a drop aid device increases efficiency of glaucoma medication when comparing changes in intraocular pressure.

A secondary objective of this study is to evaluate how often a patient missed their eye when instilling drops with various drop aids in order to assess whether drop aids can decrease medication waste, increase medication compliance, and improve visual function. Additionally, the study will analyze how satisfied the patient is with their drop aid and the likelihood they would continue to use one outside of the study. These satisfaction means will be evaluated with a patient satisfaction survey approximately 3 weeks and 6 weeks after enrollment.

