### 4.2 Study Outcome Measures

The efficiency of various drop aids will be measured through the subject’s glaucoma progression at the end of the study. On the day of enrollment, the subject’s IOP and visual acuity will be measured as part of their standard of care exam. This information is recorded as the baseline exam, and will be compared to measure the patient’s glaucoma progression at the end of the study. Subjects will be required to record the date on which they began each of their glaucoma eye drop bottles, and the date each bottle was finished in a study diary provided by the research team. Subject’s satisfaction will be measured through a brief satisfaction survey approximately 3 weeks after their enrollment. After at least 6 weeks of study participation, subject will be followed up with their regularly scheduled glaucoma provider where they will fill out a second brief satisfaction survey. The study diary will be collected and a routine eye exam will be conducted, with their IOP checked as part of a standard of care clinic visit.

All surveys were created by a member of the research team. The satisfaction survey includes five questions to assess the precision of the drop aid device, overall patient satisfaction, and willingness to use the device long term. The questions are multiple choice questions in which the patient circles the answer that best reflects their response.

Reference Section 12.0 for further statistical analysis explanations.

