#### 12.1.2. Secondary Objective: Drops Missed

Formal hypothesis: Drop aids will be effective in delivering the proper amount of drops, thereby reducing the number of missed drops for patients.

Testable hypothesis: Differences in drops missed with drop aid device compared to without drop aid device will show efficacy in drop aid device.

Null hypothesis: Patients assigned to a drop aid device will not result in less drops missed when compared to patients who are not assigned to a drop aid device.

Alternate hypothesis: Patients assigned to a drop aid device will result in minimal missed drops when compared to patients who are not assigned to a drop aid device.

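### Survey questions 3 and 4 do not say that a miss means missing the eye, so the missed-drops secondary outcome may mix off-target drops with skipped doses

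*Combined protocol and SAP*

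**What the plan says.** Section 4.1 sets a secondary objective to "evaluate how often a patient missed their eye when instilling drops with various drop aids", and gives its purpose as "in order to assess whether drop aids can decrease medication waste, increase medication compliance, and improve visual function". Section 4.2.2 lists the matching outcome first: "Number of times a patient missed their eye when instilling eye drops". Both describe an aiming failure, and both name the eye.

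The hypothesis in Section 12.1.2 is looser: "Drop aids will be effective in delivering the proper amount of drops, thereby reducing the number of missed drops for patients". It does not define a missed drop.

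The data come from the satisfaction survey in Section 15.2.4. Question 3 asks "How many times did you miss instilling drops with the help of drop aid" and question 4 asks "How many times do you miss instilling drops just using your glaucoma drops". Each offers none, 1, 2, or 3 or more; question 3 adds two not-applicable choices. Section 4.2 gives the intent: "The satisfaction survey includes five questions to assess the precision of the drop aid device", along with satisfaction and willingness to use the device long term.

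The home diary (Section 15.2.3) has fields for medication name, start date and end date only. The survey is given by phone at week 3 (Section 9.3.1) and in person at the final visit (Section 9.3.2), and Section 5 allows research staff to help.

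**The concern.** The outcome names the eye and the questions do not. Without that word, a question about missing instillation can be heard in two ways: the drop was given but landed elsewhere, or the dose was not given at all. A respondent could answer for either event, or add the two together.

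The events mean different things for the aims in Section 4.1. An off-target drop is an aiming problem in a patient who is trying to take the dose, and it uses up medication. A skipped dose is an adherence problem, and it uses none. If answers mix the two, a difference between groups cannot be assigned to aim, and the absence of a difference cannot be taken to mean that aim is unchanged. Because question 4 has the same gap, the comparison with the no-device group is exposed as well.

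**Working it through.** The plan gives no figure for this outcome. Its only sample-size figure is 4 groups × 10 = 40, set by budget (Section 12.2). The check is therefore mainly a comparison of texts.

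**Step 1: definition against instrument**
- Sections 4.1 and 4.2.2: the event is missing the eye.
- Section 12.1.2: "thereby reducing the number of missed drops for patients", which is not tied to the eye.
- Section 15.2.4, questions 3 and 4: missing instillation, with no mention of the eye and no definition.

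The plan's own clear wording was not carried onto the form.

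**Step 2: can another source separate the events?** The diary cannot, because bottle dates count neither event. Sections 5, 9.3.1 and 9.3.2 provide for staff contact, but neither they nor the form contains a script or definition.

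**Step 3: do the events act differently on drop use?** This is an illustration with assumed inputs: one eye, one drop per dose, 42 days (the 6-week minimum in Section 2), and every off-target drop repeated. The 2 to 3 uses a day come from background text on bottle life in Section 3.2 and are not a dosing rule for subjects.
- Planned drops: 2 × 42 = 84, or 3 × 42 = 126.
- Three off-target drops, each repeated: 84 + 3 = 87 (+3.6%), or 126 + 3 = 129 (+2.4%).
- Three skipped doses: 84 − 3 = 81 (−3.6%), or 126 − 3 = 123 (−2.4%).

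Bottle use moves in opposite directions, yet a respondent counting either event gives the same answer. An off-target drop that is not repeated leaves bottle use unchanged.

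**Step 4: can the distortion be sized?** Not from the documents. They give no rate of off-target drops, no rate of skipped doses and no information on how respondents read the items. To show how far the result depends on these unknowns, assume that 70% of controls and 30% of device users have at least one off-target drop, that all respondents count both events, and that a respondent has an independent chance q of at least one skipped dose. The reported proportion is then 1 − (1 − p)(1 − q).

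With the same q in both groups, the true 40-point difference becomes 40 × (1 − q). Power is for 10 against 30 patients, two-sided 0.05, normal approximation:

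| q | Control | Device | Difference | Power |
|---|---|---|---|---|
| 0 | 70% | 30% | 40 points | 0.62 |
| 0.2 | 76% | 44% | 32 points | 0.41 |
| 0.4 | 82% | 58% | 24 points | 0.25 |
| 0.6 | 88% | 72% | 16 points | 0.13 |

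With unequal q the error can go either way:
- q = 0.2 in control and 0.6 with a device: (1 − 0.3 × 0.8) − (1 − 0.7 × 0.4) = 0.76 − 0.72 = 4 points.
- q = 0.6 in control and 0.2 with a device: (1 − 0.3 × 0.4) − (1 − 0.7 × 0.8) = 0.88 − 0.44 = 44 points.

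These are not estimates for this trial. They show only that the same true effect can give very different reported differences.

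**The case against.** The strongest reply is that context settles the meaning. Question 3 ties the miss to using the aid and question 4 to using the bottle alone, which suits an aiming failure better than a forgotten dose. Question 2, just before, is about ease of instilling. Section 4.2 says that precision is what the survey assesses, and a staff member who completes the form can explain the question.

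Much of this stands. A reader might infer that the items plainly ask about skipped doses. The documents do not support that: the aiming reading is available and was evidently intended. What remains is ambiguity. Respondents do not see Section 4.2, and staff help without a script may vary from one call to the next.

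Three further inferences also go too far:
- *That the two events have opposite effects on waste.* A skipped dose wastes nothing. The opposition is in drop use and bottle life.
- *That three skipped doses scoring the same as dozens of off-target drops shows the harm.* That comes from the top category of *3 or more*. With perfect wording, 3 and 63 off-target drops would still score alike.
- *That the week-3 contact could lower the score with no change in aim.* The schedule of events lists re-teaching of device use at that contact, so aim may change too. Compliance there may also mean compliance with the device.

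Nor is this count the only evidence on waste: bottle dates are collected, and Section 12.3 compares time to completion of drops with controls.

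**Conclusion.** The point holds as a mismatch between a defined outcome and an ambiguous instrument. Questions 3 and 4 are the only source for item 1 of Section 4.2.2 and for hypothesis 12.1.2, and as worded they allow skipped doses into a count meant for off-target drops. A mixed count would not answer that hypothesis cleanly, and would not serve the waste or compliance aims of Section 4.1.

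The size is unknown. It depends on how many respondents take the other reading and on how often doses are skipped in each group, and the documents give neither. If every respondent takes the intended meaning, there is no distortion. The conclusion also assumes that no interviewer script exists outside the text available for review. The effect is confined to a secondary outcome; the primary IOP comparison does not use these items. The change is still worth making, because it is cheap and answers collected under the present wording cannot be separated afterwards.

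**What to change.** Reword questions 3 and 4 to name the event, for example: *When putting in your drops [with the drop aid / without a drop aid], how many times did a drop miss your eye? Do not count doses you skipped.* Read the same words over the phone and in clinic. Use only these answers for item 1 of Section 4.2.2 and for hypothesis 12.1.2, and state in Section 12.1.2 that a missed drop is one that missed the eye. The with-aid and without-aid pair can stay.

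Optionally, add one separate question on scheduled doses not taken and report it as compliance, outside the missed-eye outcome. Section 4.2, which says that the survey has five questions, would then need updating.

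The cost is an amended form that needs IRB acknowledgement. Surveys already collected could not be pooled with new ones on these two items and would have to be reported separately.
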